Cervical cancer screening standard of care:

La Liga mobile units are set up close to busy locations (e.g., a market) in pre-selected communities. Screening is offered 9 am-3:00 pm every weekday for 1-2 weeks per community. Women receive Pap, VIA, breast, thyroid and rectal exams and each clinical encounter typically lasts 15 min (see Table 1). La Liga also has two central administrative offices and clinics (detection centers) where cancer-related screening and treatment is offered by health providers including expert colposcopists, and where administrative staff are based. Training has been conducted on use and reprocessing of the Pocket device, however it is not currently in use in clinics.

Currently, if VIA+ (any evidence of whitening after application of acetic acid; determined at the same time as the exam), women are advised during screening that follow-up clinical evaluation with a medical expert (colposcopist) is required, however no referrals for care are made until Pap smear results are received in about 30 days, unless there is a suspicion of cancer. Patient information and the diagnosis is entered into an electronic database at La Liga (WebLiga). La Liga staff contact women who screen positive and are diagnosed with cervical cancer or pre-cancer to schedule follow-up appointments for care, management and treatment. If the woman misses the colposcopy appointment, La Liga staff call to reschedule. After three attempts at rescheduling, the woman is considered lost-to-follow-up.

Table 1: Standard of care and proposed intervention (mIVAA)

Standard of care	mIVAA
Screen with VIA (IVAA) and Pap in MUs	Screen with VIA, Pap and mIVAA (digital imaging device component) in MUs
No expert review	Expert reviews digital images of the cervix remotely using mIVAA's telemedicine component and refers for follow-up appointments for care, management and treatment, if positive
Refer women for colposcopy based on Pap results 3-4 weeks later	For any women not referred already, refer if needed based on Pap results, per standard of care

Perform diagnostic colposcopy and biopsy and treat, if possible, at central La Liga clinic in Lima	Perform confirmatory colposcopy and biopsy and treat, if possible, at central La Liga clinic in Lima
Additional visits to complete treatment, per standard of care.	Additional visits to complete treatment, per standard of care.

Description of intervention and framework for development:

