- Once health providers and staff are consented, screened and enrolled, we will work with La Liga to train midwives, nurse technicians who worked in mobile units, and colposcopists to use mIVAA (including use of the Pocket) and on research protocols including maintaining confidentiality of participant

data.

Midwives with assistance from nurse technicians

Activity 1: Use mIVAA system during VIA with consenting women

For each woman who consents to the use of mIVAA system, midwives will:

- Attempt to capture digital images of the cervix with mIVAA.
- Enter relevant clinical notes in mIVAA.
- Use mIVAA to send images of the cervix and of the VIA results form for each patient to participating expert colposcopist for evaluation of these images to evaluate the need for a management plan,
- For women with a positive VIA or suspicion of cancer, follow-up clinical evaluation with a colposcopist in a La Liga detection center will be scheduled based on feedback received from these same colposcopists as per La Liga's institutional protocols.
- For women without suspected lesions, further referrals may be made according to standard of care based on Pap results when available, and if positive.

Activity 2: Provide feedback on mIVAA through a brief survey and interviews, and/or an individual or group interview. Discussions will assess feedback and satisfaction with mIVAA. Individual or group interviews may be completed in person, by phone or by Zoom. The interviews will be audio recorded using an encrypted digital audio recorder, voice recording app on tablet or using Zoom's audio recording function.

Study staff will document in Spanish La Liga provider and staff feedback, and translate to English for analysis and inclusion in any publications. Interviews may be audio recorded, transcribed and translated.

Colposcopists

Activity 1: Use mIVAA system to access patient cervical screening documentation and communicate with midwives and staff at mobile unit.

For each patient, expert colposcopist will:

- Provide feedback on whether the patient should have a follow-up clinical evaluation.
- Rate quality of cervical image.

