Activity 2: Provide feedback on the use of mIVAA through a survey, brief interviews, and/or an individual or group interview. Discussions will assess feedback and satisfaction with the mIVAA system. Individual or group interviews may be completed in person, by phone or by Zoom. The interviews will be audio recorded using an encrypted digital audio recorder, voice recording app on tablet or using Zoom's audio recording function.

Study staff will document in Spanish La Liga provider and staff feedback, and translate to English for analysis and inclusion in any publications. Interviews may be audio recorded, transcribed and translated.

Aim 2: To evaluate effectiveness of mIVAA by comparing the attendance for follow-up clinical evaluation among women screened with mIVAA compared to historical data on women referred for follow-up without mIVAA.

Hypothesis: Use of mIVAA will result in a 13.5% increase in the proportion of screen-positive women completing follow-up clinical evaluation, compared to situations where mIVAA is not used.

Methodology:

For this aim, we will enroll approximately 200 VIA+ women attending any one of five La Liga mobile units for cancer screening, and approximately 18 La Liga health providers and administrative staff. As per standard of care, VIA+ women would be referred for follow-up care. Improving attendance of follow-up care is a primary objective of the study.

As part of the evaluation, we will:

- Assess mIVAA for image quality, network stability, challenges with image transmission, ability and time to reach experts and receive feedback from experts (two-way communication between health providers).
- Assess provider feedback and satisfaction from the use of mIVAA
- Document timing of providing women who screen positive on VIA with colposcopist evaluation of cervical images and management plans based on digital cervical images, and follow-up appointment for confirmatory colposcopy and biopsy.
- Collect survey data from women to identify correlates of follow-up.
- Document rate of follow-up care among women who are referred for management and treatment.
- Abstract historical data from medical records including: clinical notes on Pap results; for women who screened positive on VIA, rates of attending follow-up appointments and colposcopist evaluation; and possible reasons for not attending follow-up appointments.

Study activities with enrolled women

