The Pocket is an FDA approved device. The Pocket's outer shell is made out of medical grade ABS plastic. Medical grade and biocompatible adhesives (Loctite 4011) are used to seal the device and prevent infiltration of water and bodily fluids. The edges of the probe face are also chamfered to avoid a sharp edge so there should be minimal risk of abrasion caused by the probe with the pressure exerted.

Finally, the Pocket will undergo cleaning and high-level disinfection per the instructions for use prior to use in a patient. The reprocessing procedures have been validated by an independent third-party laboratory, Nelson Labs, and found to be a safe and effective way of infection control.

Benefits:

Women receiving the intervention may be referred to follow-up care sooner than those who do not receive the intervention (standard of care).

For participants who are La Liga health providers or administrative staff, there are no direct benefits for taking part in the study. However, they may feel a sense of satisfaction in helping inform a process that may improve future cancer screening and treatment programs (for the community), provide faster care to patients, improve patient follow-up care, and reduce deaths from this disease in the future.

11. Costs to the Subject:

There are no costs to the participants of this study.

12. Data Analysis & Statistical Considerations:

Sample size justification: With the proposed sample size of 200 women/group, we are powered to detect a difference of 13.5% or higher in loss to follow-up with 80% power at 5% level of significance. This difference of 13.5% corresponds to an odds ratio around 1.8, or a Cohen's η around 28%. For the in-depth interviews, sample size reflects number of interviews required to achieve saturation of themes. Namey et.al estimate that 8-16 interviews are needed to achieve 80-90% saturation, respectively.

Statistical analysis plan:

Quantitative data analysis will be conducted using STATA statistical software, SAS, JMP and/or MS Excel. Descriptive statistics will be generated to assess and quantify statistical properties of all the relevant variables (mean, median, standard deviation,

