etc.). The difference in the proportion of women attending follow-up clinical visits between the two arms will be calculated to estimate the intervention effect at 5% level of significance level. Baseline covariates will be modeled using multivariable logistic regression to determine patient characteristics associated with loss-to-follow-up. Measures of predictive power (like R-square) and goodness of fit tests (like the Pearson chi-square) will be used to assess the fit of the regression model.

As part of the qualitative analysis plan, we will conduct applied thematic analysis on the observation notes and interview transcripts. Electronic files will be uploaded into QSR NVivo--software that supports coding and finer level re-coding of text data that enables researchers to explore how concepts fit by developing and modifying a hierarchical coding index. Thematic analysis will be conducted via an iterative process of data collection and analysis that utilizes four interrelated steps: reading; coding; data display; and data reduction. The team will use a codebook of a priori, structural codes based on the interview guide, and then a second round of coding, i.e. content coding, will be conducted to identify additional themes, ideas, or concepts. Twenty percent of transcripts will be coded by 2 team members, inter-rater reliability assessed, and discussions held to resolve coding discrepancies. We will create a summary of each interview and look across interviews for commonly named problems and solutions for each step of image acquisition, transfer, and interpretation.

Data will be summarized in the following areas: Core functionality (including expectations, and communication formats), data analytics, storage and availability, (3) Security, hosting and privacy, 4) Mobile delivery platform, 5) Monitoring and maintenance, 6) Hardware, equipment, power and connectivity needs.

In interviews with women in aim 1 and 2, we will assess satisfaction with the (a) overall experience, (b) timeliness of evaluation of cervical images and management, and (c) any barriers to attending future clinical visits.

Evaluation outcomes are summarized in table below.

Primary outcome - Efficacy

- Percentage of referred women who are lost to follow-up in intervention versus control arm

Secondary outcomes - Process

- Percentage of women approached who consented to participate in study
- Percentage of women approached who refused to participate in study

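### Section 12 declares and powers on loss to follow-up but estimates the effect on attendance, and the only stated loss rule does not make the two complements

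*Combined protocol and SAP*

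**What the plan says.** **Loss to follow-up.** The primary efficacy outcome in Section 12 is "Percentage of referred women who are lost to follow-up in intervention versus control arm", and Sections 2 and 3 give the same outcome. The sample size paragraph of Section 12 says "we are powered to detect a difference of 13.5% or higher in loss to follow-up". The covariate model in the statistical analysis plan also has loss as its outcome.

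**Attendance or completion.** The only sentence in Section 12 that compares the arms is "The difference in the proportion of women attending follow-up clinical visits between the two arms will be calculated to estimate the intervention effect", at the 5% level. In Section 5, the Aim 2 hypothesis is "Use of mIVAA will result in a 13.5% increase in the proportion of screen-positive women completing follow-up clinical evaluation", and the methodology beneath it adds "Improving attendance of follow-up care is a primary objective of the study".

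**What counts as lost.** The only statement is in Section 5, in the description of standard care: "If the woman misses the colposcopy appointment, La Liga staff call to reschedule", and then "After three attempts at rescheduling, the woman is considered lost-to-follow-up". No time limit is attached. In the mIVAA arm, follow-up is scheduled "based on feedback received from these same colposcopists as per La Liga's institutional protocols", and no separate definition of loss is given.

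**The concern.** The declared primary outcome has no between-arm analysis written for it, and the quantity that is analysed is not the declared outcome. This would be harmless if loss were defined as non-attendance, but it is not.

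Under the three-attempt rule there is a third state: the woman has missed her appointment and fewer than three attempts have been made. She has not attended and is not yet lost. Nothing in the plan classifies her or sets a date by which she must be classified.

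The third state need not be equally common in the two arms. Controls are abstracted from older records, where rescheduling has probably run its course. mIVAA women are followed prospectively with no stated cut-off, so late enrollees may still be in the rescheduling process when data are closed. Each unresolved mIVAA woman lowers the loss percentage without adding an attendance. The study could then report lower loss, its declared outcome, with no gain in what Aim 2 sets out to improve.

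**Working it through.** **Inputs from the documents.** 200 women per group, 80% power, 5% level and a 13.5-point difference (Section 12). 77% of referred women do not show up (Section 4), and the same figure is given for VIA-positive women (Section 2), so control attendance is 100 − 77 = 23%. Sidedness is not stated; two-sided is assumed.

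**Input not in the documents.** The unresolved share, meaning women neither attended nor lost. It is assumed below and shown over a range.

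**Step 1. The plan's own figure.** With the stated effect size of 0.28, n = 2(1.960 + 0.842)² / 0.28² = 200.2 per group, so 200 reproduces. A 13.5-point difference has odds ratio 1.80 and effect size 0.281 at a baseline near 70%. At the documents' 77% (77% vs 63.5%), the odds ratio is (0.77/0.23)/(0.635/0.365) = 1.92 and power is 84.2%. The power statement is not at fault.

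**Step 2. When the scales agree.** If loss is 100% minus attendance on one denominator, 77% vs 63.5% lost and 23% vs 36.5% attending are the same comparison. Power is 84.2% on both, and the p-value is the same.

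**Step 3. When they separate.** Under the three-attempt rule, lost = 100% − attended − unresolved. Take 46/200 attending in each arm, so the attendance difference is 0 (p = 1.00). Let 20 mIVAA women (10%) and no control women be unresolved:

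- Lost: control 154/200 = 77%; mIVAA (200 − 46 − 20)/200 = 134/200 = 67%.
- Pooled proportion 288/400 = 0.72; SE = √(0.72 × 0.28 × 2/200) = 0.0449.
- z = 0.10/0.0449 = 2.23, p = 0.026.

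**Step 4. Range.** The probability of a significant loss contrast favouring mIVAA is Φ[(d − 1.96·SE₀)/SE₁]. Here d is the difference in loss, SE₀ the pooled and SE₁ the unpooled standard error, with 200 per arm. Attendance is 23% in both arms in every row.

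| Unresolved, control | Unresolved, mIVAA | Loss, control | Loss, mIVAA | Probability |
|---|---|---|---|---|
| 0% | 0% | 77% | 77% | 2.5% |
| 5% | 5% | 72% | 72% | 2.5% |
| 5% | 7.5% | 72% | 69.5% | about 8% |
| 0% | 5% | 77% | 72% | 21% |
| 0% | 10% | 77% | 67% | 61% |

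For the third row: SE₀ = √(0.7075 × 0.2925 × 2/200) = 0.0455, SE₁ = 0.0455, and (0.025 − 0.0892)/0.0455 = −1.41, giving 0.079.

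The difference between the unresolved shares drives the bias. A shared level does not bias the contrast and costs only a little power: with attendance truly 23% vs 36.5% and equal unresolved shares of 5%, 10% or 20%, power on loss is 81.2%, 79.0% or 77.2%.

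**The case against.** The strongest reply is that the documents plainly mean loss to be non-attendance. The 77% who do not come is presented as the attrition to be reduced, the same 13.5% serves both measures, and attendance is called a primary objective. The three-attempt sentence describes clinic call-back practice and is not offered as an endpoint definition. The items listed in Section 5 for abstraction from historical records include attendance and reasons for not attending, but not rescheduling attempts (the list may not be exhaustive). Read this way, there is one test and one p-value.

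Most of this stands as an account of intent. It does not close the gap, because no sentence equates loss with non-attendance and the three-attempt rule is the only definition a data abstractor would find.

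Three stronger readings are tempting and not supported.

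- A reader might infer two competing primary tests and an inflated error rate. Section 12 specifies one between-arm comparison, on attendance. The model for loss looks for patient characteristics and does not compare arms.
- A reader might infer that control women who were never scheduled would escape being counted as lost and so hide a real benefit. The documents do not say such women are not lost, and they may fall outside the referred denominator altogether.
- A reader might take the 21% and 61% as expected error rates. They require every unresolved woman to be in the mIVAA arm, which no figure in the documents supports.

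A further objection is sound: counting unresolved women as non-attenders without a common follow-up period would penalise late mIVAA enrollees. The fix has to include that period.

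**Conclusion.** The mismatch is real and sits in the text: the outcome that is declared and powered is not the one analysed, and the only stated loss rule does not make them complements. The damage is conditional. It arises only if the declared outcome is reported by the three-attempt rule and the unresolved share differs between arms. On an assumed 10% versus 0%, loss differs by 10 points (p = 0.026) with identical attendance. On 7.5% versus 5%, the chance of a significant result favouring mIVAA is about 8%, against 2.5% with equal shares. If no woman is unresolved and one denominator is used, the issue is wording only. The sample size needs no change on this account. The correction is worth making because it costs little and removes a way for the declared outcome to improve without more women being seen.

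**What to change.** In the primary outcome line and power statement of Section 12, and in the outcome sentence of Sections 2 and 3, replace loss to follow-up with not having attended a documented colposcopist evaluation. This is the exact complement of the attendance proportion that Section 12 already compares. In the same place:

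- name one denominator (the documents variously use referred women, screen-positive women and women) and apply it to both arms;
- set one period after screening, the same for mIVAA and historical control women;
- count every other woman as not attended, including those never reached or still being rescheduled when the period ends;
- state the 13.5 percentage points on this measure.

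Loss by the three-attempt rule, and the share neither attended nor lost, can be reported descriptively by arm if attempts are recorded.

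**Cost.** A few sentences and no extra women or visits, since attendance is already to be taken from records in both arms. The descriptive loss line may need one added abstraction field. The downside is that women still being rescheduled at the cut-off count as non-attenders, in both arms alike.

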mHealth-supported Telecolposcopy for Cervical Cancer Programs in Low-resource Settings: Evaluation (mIVAA)

NCT04421131

Document Date: May 21, 2021

1. Protocol Title:

mHealth-supported telecolposcopy for cervical cancer programs in low-resource settings: Evaluation

2. Research Abstract

Our long-term goal is to facilitate early cervical cancer prevention and treatment behaviors that are critical for positive clinical outcomes such as reduced cancer progression and increased survival.

The cervical cancer prevention cascade involves several touchpoints. For instance, women screened with visual inspection with acetic acid (VIA) and suspected to have precancerous or cancerous lesions require additional visits with trained ob-gyn specialists/colposcopists who can conduct further clinical evaluation (e.g., using colposcopy or biopsy). In Lima, Peru, our study partners, Liga Contra el Cáncer-Perú (La Liga) use mobile units to provide community-based cervical cancer screening with VIA and/or Pap. In addition, they provide follow-up clinical evaluation at their brick and mortar clinics (detection centers) in Lima for women who are VIA+ and/or Pap+. However, approximately 77% of VIA+ women screened by La Liga in community settings do not present for follow-up clinical evaluation at one of La Liga's detection centers.

To address this issue, we seek to develop and evaluate mIVAA (mobile Inspección Visual con Ácido Acético – Spanish for Visual Inspection with Acetic Acid (VIA). mIVAA is described in the intervention section.

The central hypothesis is that use of mIVAA will increase the proportion of VIA positive women who complete follow-up clinical evaluation compared to VIA positive women in situations in which mIVAA was not used, thus potentially improving cervical cancer treatment and survival rates. The study will collect qualitative and quantitative data to examine the feasibility and preliminary impact of mIVAA on reducing attrition for follow-up clinical evaluations. The primary outcome is the percentage of referred women who are lost to follow-up in intervention versus control arm. Secondary outcomes include provider and patient satisfaction with the mIVAA system, and decisional conflict about follow-up. Multivariable modeling will examine correlates of follow-up.

Research Summary**3. Purpose of the Study:**

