Our long-term goal is to facilitate early cervical cancer prevention and treatment behaviors that are critical for positive clinical outcomes such as reduced cancer progression and increased survival.

In the short-term, we seek to develop and evaluate mIVAA (mobile Inspección Visual con Ácido Acético – Spanish for Visual Inspection with Acetic Acid (VIA)). mIVAA is described in the intervention section.

The central hypothesis is that use of mIVAA will increase the proportion of VIA positive women who complete follow-up clinical evaluation compared to VIA positive women in situations in which mIVAA was not used, thus potentially improving cervical cancer treatment and survival rates. The study will collect qualitative and quantitative data to examine the feasibility and preliminary impact of mIVAA on reducing attrition for follow-up clinical evaluations. The primary outcome is the percentage of referred women who are lost to follow-up in intervention versus control arm. Secondary outcomes include provider and patient satisfaction with the mIVAA system, and decisional conflict about follow-up. Multivariable modeling will examine correlates of follow-up.

This study has two specific aims:

Aim 1: To pilot test mIVAA in a community-based setting in Peru.

Aim 2: To evaluate effectiveness of mIVAA by comparing the attendance for follow-up clinical evaluation among women screened with mIVAA compared to historical data on women referred for follow-up without mIVAA.

4. Background & Significance:

Cervical cancer is the leading cause of death among women of reproductive age in Peru. Every 5 hours, a woman in Peru dies from cervical cancer. [13] Development of cervical cancer is preventable when precancerous lesions are detected and treated. However, precancerous lesions are typically asymptomatic and, in absence of preventative screening, cancers are detected at advanced incurable stages. In Peru, 80% of cervical cancer cases are detected at advanced stages. [1]

In low-resource settings, Visual Inspection with Acetic acid (VIA) and Pap smears (Pap) are widely used as a primary screening approaches due to their scalability. Both VIA and Pap have poor sensitivity, and where resources allow, are coupled with a more specific evaluation step such as colposcopy, the visualization of the cervix using a low-powered microscope to determine whether the woman should be treated or not, and/or biopsy.

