A key barrier to implementing colposcopy, especially in rural and remote communities, is low access to expert colposcopists trained to evaluate cervical images. As a result, women who screen positive in community settings are often referred to distant health facilities with expert colposcopists for further clinical evaluation. The burden of follow-up contributes to high rates of post-referral attrition and failure of women to receive appropriate treatment. [2-8]

Liga Contra el Cáncer-Perú (La Liga), a collaborating institution on the study, has five mobile units (MUs) traveling to communities across Lima and Callao to offer cervical cancer screening services. Each mobile unit consists of a midwife who performs the Pap screening tests and VIA, and a nursing technician who supports administrative tasks, data entry, and triage. Currently, many districts served by MUs have low-income

populations. MUs screen between 200-800 women each per month with 10% of women referred for follow-up colposcopy. La Liga's administrative data indicate that 77% of the women referred do not show up for a follow-up appointment.

Hence, strategies for reducing post-referral attrition are vital for improving rates of diagnosis, treatment, and survival. One strategy is to expedite the decision on whether follow-up is needed, by improving women's access to expert colposcopists at the location of the primary screening (i.e., in communities) using telemedicine.

Given the rapidly growing mobile network infrastructure in Peru, the use of mIVAA represents a key opportunity to bypass the need for stationary systems (e.g., computers), and costly fixed broadband connections associated with traditional telemedicine infrastructure to achieve scalability of enhanced visual inspection to rural and remote settings. [9] This proposal brings together a multidisciplinary team at Duke University, USA with expertise in mHealth, cervical cancer, and implementation science, in close partnership with two Peruvian organizations, Liga Contra el Cáncer-Perú (The League against Cancer-Peru) and Medical Innovation & Technology.

BIBLIOGRAPHY

1. Vallejos, C., *National plan for prevention, early detection, and cancer control in Peru*. Am Soc Clin Oncol Educ Book, 2013.
2. Aguilar, A., et al., *Control of cervical cancer in Peru: Current barriers and challenges for the future*. Mol Clin Oncol, 2016. **5**(2): p. 241-245.

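### The primary outcome counts referred women, the hypothesis and mIVAA enrolment count VIA-positive women, and the controls are described three ways; the plan does not say whether these are one population

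*Combined protocol and SAP*

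**What the plan says.** **Outcome and analysis.** The primary outcome in section 12 is "Percentage of referred women who are lost to follow-up in intervention versus control arm". The analysis sentence in the same section gives no denominator: "The difference in the proportion of women attending follow-up clinical visits between the two arms will be calculated".

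**Hypothesis and mIVAA arm.** Sections 2 and 3 state that "use of mIVAA will increase the proportion of VIA positive women who complete follow-up clinical evaluation". The Aim 2 hypothesis in section 5 speaks of screen-positive women. Sections 5 and 6 enrol about 200 VIA-positive women, and consented women who are VIA-negative do not continue.

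**Who is referred.** Aim 2 Methodology says that VIA-positive women would be referred under standard of care. The standard-of-care text in section 5 says that no referral is made before the Pap result, at about 30 days, unless cancer is suspected. Table 1 bases standard-of-care referral on Pap. In the mIVAA column it bases referral on a positive expert review, with Pap as a second route.

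**Who the controls are.** Aim 2 (sections 3 and 5) uses "historical data on women referred for follow-up without mIVAA". The abstraction item under Aim 2 Methodology concerns women positive on VIA. The paragraph on medical record abstraction takes 200 women screened at a mobile unit before mIVAA, with no VIA or referral condition. Section 6 has no criteria for controls.

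**Baseline figures.** Section 2 says that "approximately 77% of VIA+ women screened by La Liga in community settings do not present for follow-up clinical evaluation"; section 4 says that "77% of the women referred do not show up for a follow-up appointment". Section 4 has "10% of women referred for follow-up colposcopy"; Aim 2 puts VIA positivity at about 10%.

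**The concern.** Referral happens after screening, and mIVAA is designed to change how it is decided. If some VIA-positive women are not referred, restricting each arm to referred women selects on something that the intervention affects. The selection rule would be Pap or suspicion of cancer in the controls, and expert review followed by Pap under mIVAA. A difference in loss to follow-up could then arise, in either direction, because the denominators hold different kinds of women.

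The composition can differ too. Section 2 describes follow-up evaluation at detection centers "in Lima for women who are VIA+ and/or Pap" positive, so referred historical women can include VIA-negative, Pap-positive women. Their counterparts under mIVAA are not enrolled.

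At stake is the primary estimate: two analysts following different parts of the text could draw different control records and divide by different totals.

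**Working it through.** **1. The plan's own figure.** Section 12 states 200 per group, 80% power, 5% significance, a 13.5% difference, an odds ratio near 1.8 and a Cohen effect size near 28%. A two-sided test is assumed.
- Detectable arcsine effect size: (1.960 + 0.842) × √(2/200) = 0.280, which matches.
- The section states no baseline. Assuming loss of 70% versus 56.5%, the pooled two-proportion formula gives n = 200 per group and an odds ratio of (0.70/0.30)/(0.565/0.435) = 1.80.
- With the documents' 77% versus 63.5%, n = 179 and power at 200 per group is 84%.

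The sample-size arithmetic reproduces; the question is whom the 200 per group represent.

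**2. Does the text make the groups identical?** Aim 2 Methodology implies that it does. Table 1 implies that it need not, because both columns make referral conditional. The colposcopist also advises, patient by patient, whether follow-up evaluation is needed (section 5, Aim 2), so an enrolled VIA-positive woman might not be referred. No share referred is given for either arm.

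**3. Illustration with no true effect, both arms restricted to referred women as section 12 states.**
- From the documents: 23% of VIA-positive women attend (100% − 77%); 200 per arm.
- Assumed: share referred f; 6% attendance among women not referred; the same 23% and 6% in both arms; no VIA-negative controls.
- Attendance among referred women = [0.23 − (1 − f) × 0.06]/f.

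| f | Referred | Attendance among referred | Loss |
|---|---|---|---|
| 1.0 | 200 | 0.23 | 77.0% |
| 0.9 | 180 | (0.23 − 0.006)/0.9 = 0.2489 | 75.1% |
| 0.8 | 160 | (0.23 − 0.012)/0.8 = 0.2725 | 72.75% |
| 0.5 | 100 | (0.23 − 0.030)/0.5 = 0.40 | 60.0% |

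- Equal shares in the two arms: difference 0, rejection rate 5%.
- 80% of controls and 90% of mIVAA women referred: 75.11 − 72.75 = 2.4 points against mIVAA. The pooled loss is 0.74 and the standard error √[0.74 × 0.26 × (1/160 + 1/180)] = 0.0477, so the expected z is 0.0236/0.0477 = 0.50 and the chance of two-sided p<0.05 is 8%. Swapping the shares reverses the sign.
- If 16% rather than 6% of non-referred women attend, losses are 1 − (0.23 − 0.032)/0.8 = 75.25% and 1 − (0.23 − 0.016)/0.9 = 76.22%, a shift of 1.0 point.
- A wider gap gives more: 50% versus 90% gives 75.1 − 60.0 = 15.1 points at the 6% assumption. Nothing in the documents indicates a gap of that size.

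**4. What an all-VIA-positive denominator costs.** Suppose 36.5% of referred mIVAA women attend (23% + 13.5 points), against 23% of all VIA-positive controls, with 200 per arm.

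| mIVAA women referred | Cleared women never attend | 6% of cleared women attend |
|---|---|---|
| 90% | 0.365 × 0.9 = 0.3285; power 59% | 0.3285 + 0.1 × 0.06 = 0.3345; power 64% |
| 80% | 0.365 × 0.8 = 0.292; power 29% | 0.292 + 0.2 × 0.06 = 0.304; power 39% |

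**The case against.** The best defence is that the authors treat referred and VIA-positive women as one group. They attach 77% non-attendance and 10% frequency to both. The standard-of-care paragraph can be read as describing when referral happens rather than who receives it: the same sentence says that VIA-positive women are told follow-up is required, and section 10 describes the benefit as earlier referral. Section 12 also applies one denominator to both arms. This stands as evidence that the groups may largely coincide. It does not settle the matter, because Table 1 makes referral conditional in both columns and the control-abstraction paragraph has no matching condition.

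A second defence is that referred women are a coherent denominator. The programme's loss rule, three failed rescheduling attempts after a missed appointment, presupposes an appointment, and section 4 names attrition after referral as the target. That also stands, and it is why the referred-only result should not simply be discarded.

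Two stronger readings are tempting but unsupported.
- A reader might infer from the Aim 2 task list that referred mIVAA women will be set against all VIA-positive historical women, which could create a large false benefit. That list governs data collection; the outcome definition restricts both arms.
- A reader might infer that the 200 controls are unselected, leaving about 20 VIA-positive women at 10% positivity and little power. Aim 2 calls the controls referred, the abstraction item calls them VIA-positive, and section 12 powers on 200 per group. The secondary outcome on VIA positivity by arm does not help this reading: all 200 mIVAA women are VIA-positive, so it needs counts from outside the 200 in both arms.

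**Conclusion.** The concern holds as a defect in the definition of the primary comparison and should be fixed; confidence is medium. The plan leaves open whether referred and VIA-positive women are the same group in each arm, and which records make up the control group. If they are the same, there is no bias and no loss of power. If not, the denominator is formed after the intervention acts and by different routes, and the bias can go either way.

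Its size cannot be derived from the documents. The 2.4-point illustration is small against the planned 13.5 points, and rests on assumed referral shares and assumed attendance among non-referred women. It also leaves out VIA-negative controls, so it does not capture the whole mismatch. The planned outputs would not fully show which case applied: section 12 lists the percentage of mIVAA women judged suspicious by the expert, a partial proxy for one arm, but not the percentage referred by arm.

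The lack of a calendar limit on follow-up is a separate matter, and confounding from historical controls would remain whichever denominator is used.

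**What to change.** 1. Amend the control-abstraction paragraph so that the 200 controls are VIA-positive women screened before mIVAA who meet the same age, pregnancy and hysterectomy criteria as the mIVAA arm.
2. State one denominator, applied identically in both arms. Report completed follow-up evaluation among all eligible VIA-positive women (the hypothesis population, fixed at screening) and among referred women side by side, with one definition of referred. Name the primary one before control records are abstracted.
3. Report for each arm the numbers who attended, were referred but did not attend, and were not referred, with the referral route (expert review, Pap, suspicion of cancer).
4. Reconcile the standard-of-care text and Table 1 with Aim 2 Methodology on who is referred. This review takes no position on which referral rule is right. If every VIA-positive woman is referred in both arms, one sentence saying so is enough on this item, and the two results coincide.

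The cost is protocol wording and a defined frame for drawing control records; Aim 2 already plans abstraction for VIA-positive women. The drawback is that the all-VIA-positive result counts women cleared by the expert as not attending unless they attend anyway, which dilutes a real gain among referred women (step 4 of the working). The referred-only result avoids that dilution but is open to selection, so both are needed.
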